### *Endpoints:*

1yr-OS and radiographic response rates will be estimated with exact 95% confidence intervals; with 24 patients, a 95% CI will be no more than 0.4 units wide for the main study cohort. PFS, defined as the time between treatment initiation and first occurrence of disease progression or death, will be censored at last follow-up if the patient remained alive without disease progression. OS will be determined from the time of treatment initiation until the time of death, with OS being censored at last follow-up if the patient remained alive. The Kaplan-Meier curves will be used to summarize PFS and OS and to estimate the medians.

Adverse events will be graded using CTCAE version 4.03. All subjects who initiate therapy (receive at least one dose of ipilimumab and nivolumab and/or radiotherapy) will be evaluated for safety. A Bayesian monitoring approach will be applied to assess safety throughout the Phase II trial with pre-defined stopping rules.

CONFIDENTIAL

This material is the property of the NYU School of Medicine. Do not disclose or use except as authorized in writing by the study sponsor

CONFIDENTIAL

This material is the property of the NYU School of Medicine. Do not disclose or use except as authorized in writing by the study sponsor

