### 6.6.2 Efficacy Assessment

**Local reading (investigator assessment)** will be used to determine eligibility and for participant management. Response Assessments will be performed on every brain imaging assessment performed on protocol per standard **RANO criteria**. However, due to the known for patient management, non-traditional iRANO criteria may be used.

- Refer to Appendix 3 for details on iRANO criteria, guidelines for assessing radiologic findings, and treatment algorithm for the assessment of progressive imaging findings in patients with neuro-oncological malignancies undergoing immunotherapy.

**Evaluable for objective response.** Only those participants who have measurable disease present at baseline (obtained within 14 days of Cycle 1, Day 1) scan and have received at least one dose of therapy will be considered evaluable for response. These participants will have their response classified according to the definitions stated in Appendix 3. (Note: Participants who exhibit objective disease progression or die prior to the end of cycle 1 will also be considered evaluable.)

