## 7 Statistical Plan

### 7.1 Background for Statistical Plan

*MGMT* unmethylated, elderly and poor functional status newly diagnosed GBM patients treated on recent randomized clinical trials with regimens including radiotherapy, temozolamide or bevacizumab have median survivals in the range of 6-12 months, with one study that did not enroll patients with unresectable (biopsy-only) tumors which carry poorer prognosis reporting 14 months. With standard chemoradiation, the fraction of patients alive at 1 and 2 years for *MGMT* unmethylated patients aged 70 or less with good functional status are 50% and 6%. The 1 year OS proportion for elderly and poor prognosis patients ranges from 21-32%.

With regards to hypofractionated radiotherapy in newly diagnosed GBM, the IAEA randomized trial treated elderly and poor functional status GBM patients aged  $\geq 50$  with hypofractionated RT (5 fraction) and the median OS was 8 months. In recent years, other small phase I and II studies have reported short course RT to have similar efficacy similar to standard treatment regimens in selected newly diagnosed GBM patients, although these studies did not stratify by *MGMT* methylation status. Median OS in these *MGMT* non-stratified studies ranged from 15 to 20 months.

Based on these historical measures, a 12 month (1yr-OS) of 35% will be considered non-promising in *MGMT* unmethylated, newly diagnosed GBM subjects; an increase in the 1yr-OS to 60% will be considered promising.

Most recently, a phase II randomized multicenter clinical study in patients with recurrent glioblastoma suggest that treatment with the PD-1 inhibitor pembrolizumab results in significantly prolonged overall survival when given neoadjuvantly (prior to tumor re-resection) as compared to pembrolizumab adjuvantly (after tumor re-resection). This increase in overall survival was associated with upregulated T cell-activation and Interferon- $\gamma$ -gene expression signatures and downregulation of cell-cycle related gene expression signatures in tumor cells. In this study, interferon- and T cell-pathway induction was seen in 9 of 14 tumors (64%) from patients who received neoadjuvant pembrolizumab compared to 5 of 15 tumors (33%) from patients who received pembrolizumab adjuvant-only.

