### 7.2.2 Main Study Cohort - Phase II trial design

A single-stage design will be utilized to estimate overall survival, with a hypothesized 1yr-OS of 60%= $H_1$  and 35%= $H_0$ . We will enroll 24 patients; this design has a two-sided Type I error of 0.05 and a power of 80%.

For endpoint analyses, one year will be defined as 48 weeks (8 cycles) and two years will be defined as 96 weeks (16 cycles). Patients will be evaluated for radiographic responses by conventional contrast enhanced MRI every 8 weeks. Radiographic response assessments will be determined using RANO criteria for GBM.

1yr-OS and radiographic response rates will be estimated with exact 95% confidence intervals; with 24 patients, a 95% CI will be no more than 0.4 units wide. OS will be determined from the time of treatment initiation until the time of death due to any cause, with OS being censored at last follow-up if the patient remained alive. Patients who were last known to be alive and progression-free will be censored at the latest disease assessment. The Kaplan–Meier curves will be used to summarize OS and to estimate the medians.

PFS is defined as the time between treatment initiation and first occurrence of disease progression or death, and will be censored at last follow-up if the patient remained alive without disease progression. PFS is defined as the time from the first dose of study treatment to the earlier of disease progression or death due to any cause. Patients who initiate alternate anticancer therapy in the absence of documented progression will be censored at the latest disease assessment prior to initiation of such therapy. Patients with no post-baseline disease assessments will be censored at the Cycle 1 Dose 1 date unless death occurred prior to the first planned assessment (in which case the death will be considered a PFS event). The Kaplan–Meier curves will be used to summarize PFS and to estimate the medians.

Overall response rate (ORR) is defined as the proportion of patients who achieve best overall response of complete or partial response at any time after initiation of study treatment (prior to initiation of alternate anticancer treatment). Duration of response is defined as the number of months from the time criteria are first met for either CR or PR, until the first date that PD is objectively documented. The duration of objective response will be summarized descriptively using the Kaplan-Meier method.

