#### **7.3.2 Phase II Trial Efficacy Analysis Population**

All subjects that receive at least 1 dose of study drug will be included in the primary analysis for the phase II study, including subjects in the Safety Lead-In treated at the same dose as the phase II subjects.

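### The stated maximum width of 0.4 for an exact 95% interval with 24 patients is slightly too small for the usual exact method (0.42), and the response-rate denominator is not settled

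*Combined protocol and SAP*

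**What the plan says.** Section 7.2.2 fixes the interval method: "1yr-OS and radiographic response rates will be estimated with exact 95% confidence intervals". The same sentence continues: "with 24 patients, a 95% CI will be no more than 0.4 units wide". The Endpoints paragraph of the synopsis makes the same promise: "a 95% CI will be no more than 0.4 units wide for the main study cohort". Neither place says which exact method is meant.

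The survival benchmarks are in Section 7.1: "a 12 month (1yr-OS) of 35% will be considered non-promising", and "an increase in the 1yr-OS to 60% will be considered promising". The denominator for one-year survival is in Section 7.3.2: "All subjects that receive at least 1 dose of study drug will be included in the primary analysis for the phase II study". With the planned enrolment that is 24.

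For response there are two descriptions. Section 6.6.2, repeated under the anti-tumor effect definitions in the iRANO appendix (Section 15.4), restricts who is evaluable: "Only those participants who have measurable disease present at baseline", with at least one dose received. Section 7.2.2 defines overall response rate as a proportion of patients and does not mention that restriction. The documents do not say how many of the 24 will have measurable disease at baseline.

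**The concern.** The sentence gives a method (exact), a confidence level (95%), a sample size (24) and an upper bound (0.4), so it can be checked directly. The main cohort's primary objective in the synopsis is to estimate one-year survival, and this is the plan's only statement of how precise that estimate will be. If the bound fails for the outcomes the trial expects, the plan claims a property its design does not have.

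The sentence also applies the 24-patient bound to response. If response is analysed only in patients with measurable disease, the denominator may be smaller and the bound would not apply to it.

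**Working it through.** **Inputs.** n = 24 and exact 95% intervals (7.2.2); benchmark rates 35% and 60% (7.1), so the expected numbers alive at one year are 0.35 × 24 = 8.4 and 0.60 × 24 = 14.4. One-year status is assumed known for all 24.

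**Step 1: where 0.4 comes from.** The Wald width is widest at p = 0.5:

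2 × 1.96 × √(0.25/24) = 0.4001.

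This agrees with the plan's figure. That it is the source is an inference, but the Wald interval is not exact.

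**Step 2: the Clopper-Pearson width.** For x survivors of n, the lower limit is the 0.025 quantile of Beta(x, n − x + 1) and the upper limit is the 0.975 quantile of Beta(x + 1, n − x). With n = 24:

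| Survivors | Limits | Width |
|---|---|---|
| 8 | 0.156 to 0.553 | 0.397 |
| 9 | 0.188 to 0.594 | 0.406 |
| 10 | 0.221 to 0.634 | 0.4125 |
| 11 | 0.256 to 0.672 | 0.416 |
| 12 | 0.291 to 0.709 | 0.4175 |
| 13 | 0.328 to 0.745 | 0.416 |
| 14 | 0.366 to 0.779 | 0.4125 |
| 15 | 0.406 to 0.812 | 0.406 |
| 16 | 0.447 to 0.844 | 0.397 |

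As a check on the lower limit for 12 of 24, the binomial probability of 12 or more at p = 0.29124 is 0.0250, as it should be. The width exceeds 0.40 for exactly 9 to 15 survivors, that is 37.5% to 62.5%. The largest excess is 0.4175 − 0.40 = 0.0175.

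**Step 3: how likely that range is.** The probability of 9 to 15 survivors is 47% if the true rate is 35% and 66% if it is 60%.

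**Step 4: other intervals at n = 24.** Maximum widths are 0.395 (Sterne) and 0.399 (Blaker), both exact. Mid-p (0.388) and Wilson (0.371) are not exact. Whether the bound holds therefore depends on which exact interval is meant.

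**Step 5: response.** The number evaluable is not given, so the following values are assumptions that show the range only. The maximum Clopper-Pearson width is 0.436 with 22 evaluable, 0.456 with 20, 0.507 with 16 and 0.578 with 12. These maxima occur near a 50% response rate. At low rates the width stays under 0.40: 0.379 for 4 of 20, 0.368 for 2 of 16, 0.383 for 1 of 12.

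**The case against.** The strongest reply is that the discrepancy is trivial. The bound is given to one decimal, and 0.4175 rounds to 0.4. The excess is under one percentage point at each end. The sample size comes from the test of 35% against 60%, not from interval width, and no stopping or success rule uses the figure. All of this stands, and it limits the point to a correction of a stated number. It does not make the number right: the wording sets a ceiling, and under the usual exact interval that ceiling is more likely than not to be broken if the alternative is true.

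A second reply is that the plan names no exact method and that exact intervals meeting 0.4 exist. This also stands. A reader might infer that no exact interval with 24 patients can stay within 0.4; Sterne and Blaker show otherwise. The fault is a bound that fails for the usual reading, together with a method left unnamed.

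A reader might also infer that the trial is too small because keeping every Clopper-Pearson width within 0.40 takes 27 patients (26 gives 0.4015, 27 gives 0.394). The documents do not support that, since enrolment was never set by width.

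Finally, a reader might infer that the response-rate interval must be wider than the survival interval. That is not established. Section 7.2.2 defines the rate over patients, which would keep the denominator at 24. No section says how many lack measurable disease, and the width depends on the observed rate.

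**Conclusion.** The bound is wrong as written if exact means Clopper-Pearson, which is its usual meaning. The correct maximum with 24 patients is 0.4175, or 0.42 to two decimals, and the stated 0.4 fails for 9 to 15 survivors. The conclusion rests on that reading of exact and on 24 patients with known one-year status. The consequence is minor: one precision figure is slightly favourable, and the design, the test and the decisions are unaffected.

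The response-rate part is an inconsistency between sections, not a demonstrated loss of precision. Sections 6.6.2 and 15.4 point to one denominator and Section 7.2.2 to another. Only if the evaluable subset is used, and is smaller than 24, does the 24-patient bound cease to apply; the width can then be larger, depending on the number evaluable and the observed rate.

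**What to change.** In Section 7.2.2 and the synopsis, name the interval as Clopper-Pearson and state that it is at most 0.42 wide with 24 patients. Alternatively, keep 0.4 and name an exact interval that meets it, such as Blaker (maximum 0.399). Either choice keeps the plan's commitment to exact intervals, so moving to an approximate method such as Wilson is unnecessary.

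In Section 7.2.2, state the denominator for response rate and make it agree with Sections 6.6.2 and 15.4. If it is the evaluable subset, say that the bound for 24 patients does not apply to response and that the width can be larger, depending on the number evaluable and the observed rate. Assumed evaluable counts should not be written into the protocol.

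The cost is one sentence in two places, plus one sentence on the response denominator. Enrolment, data collection and the primary test do not change.

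### Section 7.2.2 puts a PFS censoring rule in the OS paragraph, contradicting the OS rule before it, while PFS is censored at last follow-up; Kaplan-Meier OS can be biased downward

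*Combined protocol and SAP*

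**What the plan says.** Section 7.2.2 counts OS from the start of treatment to death, whatever its cause. Its first censoring rule is worded "with OS being censored at last follow-up if the patient remained alive". The next sentence reads "Patients who were last known to be alive and progression-free will be censored at the latest disease assessment". The one after that is still about OS: "The Kaplan–Meier curves will be used to summarize OS and to estimate the medians". The scan-based sentence therefore sits inside the OS text and cannot be read as the opening of the PFS paragraph.

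The PFS paragraph follows and says that PFS "will be censored at last follow-up if the patient remained alive without disease progression". Two other PFS rules in that paragraph are tied to assessments: starting another therapy censors at the latest assessment before it, and having no post-baseline assessment censors at the first dose.

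The Synopsis (Statistical Considerations, Endpoints) gives the last-follow-up rule for OS with no scan-based addition. It also censors PFS at last follow-up.

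For the primary endpoint, Section 7.2.2 sets one year at 48 weeks and says "1yr-OS and radiographic response rates will be estimated with exact 95% confidence intervals". Section 7.2.4 treats 1-year OS as binary.

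**The concern.** A patient who is alive and progression-free, and who was contacted after the last scan, has two different OS censoring dates under two consecutive sentences. The analyst has to choose, and in an open-label, single-arm trial of 24 patients that choice could be made with the outcomes in view.

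The scan rule also discards information that the protocol works to collect. Section 6.8.3 obtains vital status every 3 months by visit, telephone, e-mail or mail, with no scan needed. The rule removes known-alive time from progression-free patients only; patients who have progressed keep theirs up to last contact. Because progression-free patients are at lower risk of death, removing them early lowers the estimated survival curve.

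PFS has the opposite problem. Censoring at last follow-up treats a patient as progression-free up to a contact that may have involved no imaging.

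**Working it through.** **Design figure.** Inputs from Section 7.2.2: n = 24, 35% against 60%, alpha 0.05, power 80%. Exact binomial with success at 13 or more: P(X ≥ 13 | 24, 0.35) = 0.042 and P(X ≥ 13 | 24, 0.60) = 78.7% (normal approximation 81.6%). The stated 80% is thus reproduced as a one-sided test. Read as two-sided, as Section 7.2.2 words it, the cut is 14 or more, with upper tail 0.016 and power 65.0%. That mismatch is a separate matter; the one-sided boundary is used below.

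**Effect on Kaplan-Meier 48-week OS.** The documents give no figure, so the two rules were compared by simulation (1,500 trials of 24 per scenario).

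- From the documents: accrual over 18 months (78 weeks, Section 4.4); median time to progression 6 months (26 weeks, the standard-therapy PFS in Section 3.1.3); scans every 8 weeks.
- Assumed: exponential times; deaths only after progression; mean post-progression survival of 32.3 or 7.7 weeks, chosen to give 48-week OS of 60% or 35%; in half the scenarios, 20% of patients have their last scan before week 48.

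Mean 48-week OS, last-follow-up rule → scan rule:

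| Data cut after end of accrual | Scans | OS set at 60% | OS set at 35% |
|---|---|---|---|
| 0 weeks | continue | 60.3 → 58.8 | 35.1 → 32.8 |
| 0 weeks | 20% stop | 60.2 → 57.6 | 34.8 → 30.6 |
| 26 weeks | continue | 59.5 → 58.9 | 35.3 → 34.3 |
| 26 weeks | 20% stop | 60.1 → 58.6 | 34.8 → 32.3 |
| 48 weeks | continue | 60.1 → 60.1 | 34.8 → 34.8 |
| 48 weeks | 20% stop | 60.0 → 59.3 | 34.9 → 33.9 |

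The loss runs from 0 to 4.2 points. The zero has a plain reason: week 48 is a scan week (6 × 8), so a patient scanned on schedule and followed for at least 48 weeks is not censored before week 48. The simulation places scans exactly on the 8-week grid. With the ±7-day window, a scan taken in week 47 could still catch a patient if the cut came soon afterwards.

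**Later time points.** With the 48-week cut and scans continued, 96-week OS (the plan's 2-year OS) falls from 24.3% to 23.6% in the 60% setting and from 9.9% to 9.2% in the 35% setting, 0.7 points each. A living progression-free patient on schedule loses about 4 weeks of follow-up on average.

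**Effect on the binary proportion.** The rule matters only for a patient known alive at week 48 whose last scan was earlier. With the 48-week cut and 20% stopping scans, that is about 0.6 patients per trial of 24. If such patients are dropped, the exact one-sided p-values against 35% are:

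- None: 13/24 = 54.2%, p = 0.042.
- One: 12/23 = 52.2%, p = 0.068, a shift of 54.2 − 52.2 = 2.0 points.
- Two: 11/22 = 50.0%, p = 0.107.

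**The case against.** The strongest reply is that this is a drafting slip with little practical reach. The correct OS rule stands immediately before the disputed sentence and again in the Synopsis. The Synopsis (Study Assessments, Efficacy) continues MRI until progression or treatment discontinuation, whichever is later, so a progression-free patient who stops drug should still be scanned every 8 weeks. The primary endpoint is a proportion in all treated patients, not a Kaplan-Meier estimate. Any bias in OS is conservative. All of this stands, and it limits the size of the problem. It does not remove the contradiction, because scans can be missed, and contacts fall between scans.

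Three stronger readings are tempting but not supported:

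- A reader might infer from Appendix 1, which marks no MRI in the end-of-treatment or later columns, that progression-free patients who stop treatment would routinely be censored before week 48. The Synopsis scan rule says otherwise; this needs missed or stopped scans, or an early data cut.
- A reader might charge each affected patient at 1/24 = 4.2 points of 1-year OS. That counts a censored patient as a death (12/24, p = 0.094), which no section says. Section 7.2.2 is silent on how a patient censored before 48 weeks enters the proportion; dropping one costs about 2.0 points.
- A reader might cap the excess PFS credit at one 3-month contact interval. Nothing supports that cap: if scans continue, the excess is short, and if they stop, it can exceed one interval.

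**Conclusion.** The two OS rules are incompatible, and the scan-based one is the misplaced rule: the endpoint is death from any cause, to which progression status is irrelevant, and the Synopsis omits the scan rule for OS. The main exposure is the Kaplan-Meier OS curve, median and 2-year OS, all biased downward if the sentence is applied. For 48-week OS the effect is nil with scans continued and mature follow-up, and about 1 to 4 points in the assumed scenarios with early scan cessation or an immature cut. The primary proportion is exposed only through a patient known alive at 48 weeks with an earlier last scan; one such patient changes the conclusion only when the result sits on the boundary. The simulated sizes rest on the assumptions listed, above all the 20% who stop scans, for which the documents give no figure. The contradiction itself rests on no assumption. The PFS wording errs in the favourable direction, by an amount that cannot be bounded from the documents.

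**What to change.** In Section 7.2.2, delete the scan-based sentence from the OS paragraph so that OS is censored only at the date last known alive. State that any patient known alive at 48 weeks counts as a 1-year survivor, whatever the date of the last scan. In the PFS paragraph of Section 7.2.2 and in the Synopsis (Endpoints), replace censoring at last follow-up with censoring at the latest disease assessment; changing only one of the two would create a new contradiction.

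The cost is a few sentences in two places. No new data are needed, and sample size and design power are unchanged. PFS may look slightly less favourable.

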### 7.2.3 Phase II trial – Surgical Study Cohort

A single-stage design will be utilized to estimate overall survival, with a hypothesized rate of T-cell pathway induction of 64%= $H_1$  and 33%= $H_0$ . We will enroll 16 patients; this design has a two-sided Type I error of 0.05 and a power of 80%.

CONFIDENTIAL

This material is the property of the NYU School of Medicine. Do not disclose or use except as authorized in writing by the study sponsor

#### **7.2.4 Biomarker Analyses**

Correlative biomarker endpoints are exploratory and hypothesis generating. The correlative studies are not powered to make a formal test of the prognostic power of any biomarker. We will use non-parametric statistics (e.g. Wilcoxon, Spearman's rank correlation coefficient, Fisher's Exact test) to test the association between patients that achieve 1yr-OS and those that do not and the fraction of predicted mutation-associated neoantigens, fraction of expressed mutation-associated neoantigens, and levels of tumor-infiltrating immune populations identified by RNA-Seq between.

For the circulating Treg and MDSC biomarker study, we summarize the distributions of levels at baseline and changes from baseline using descriptive statistics and graphical displays. Changes from baseline will be examined using Wilcoxon signed rank tests for paired measurements. Logistic regression will be used to predict 1yr-OS (binary) based on baseline levels and the changes from baseline. Optimal cutpoints for changes from baseline will be estimated for the separation of those patients who are alive at 1 year compared to those who are not using the Youden Index based on the receiver operating characteristic curve.

For the tumor tissue PD-L1 and TIL assays, we will use similar descriptive analyses and summary displays to assess whether expression of PD-L1 is associated with 1yr-OS. Additional analyses will combine all of these key biomarkers in logistic models to identify potential combinations of markers to predict 1yr-OS.

Imaging features of tumor cell death and inflammation will be defined as increased contrast-enhancement on conventional MRI, and a statistically significant elevation of mean tissue sodium concentration (TSC) by at least 25% on Na MRI.

Associations between other exploratory biomarker measures from peripheral blood or tumor and clinical outcomes will also be explored graphically, and further assessed as needed by methods such as, but not limited to, logistic regression, and characterized by appropriate statistics.

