### *Sample Size:*

**Main Study Cohort:** Based on historical measures, a 12 month (1yr-OS) of 35% will be considered non-promising; an increase in the 1yr-OS to 60% will be considered promising. We will use a single-stage design and enroll 24 patients. This will provide 80% power to detect an increase in the 1-year OS from 35% to 60%, using a 0.05-level test.

**Surgical Study Cohort:** Based on historical measures, a T-cell pathway induction rate of 33% will be considered non-promising; an increase in the T-cell pathway induction rate to 64% will be considered promising. We will use a single-stage design and enroll 16 patients. This will provide 80% power to detect an increase in the 1-year OS from 33% to 64%, using a 0.05-level test.

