#### Both Study Cohorts:

We will explore the association of 1-yr OS with tumor tissue and circulating biomarkers as described in the exploratory study endpoints to identify potential biomarkers that predict response or resistance.

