Surgical Study Cohort: We will use a single stage design to assess safety, feasibility and therapeutic efficacy of nivolumab and ipilimumab with the first dose being administered pre-operatively and continued post-operatively in conjunction with HFRT. We will enroll 16 subjects in this cohort. Monitoring of toxicity attributable to study treatment will be continually assessed (see Primary Safety Endpoints, Section 3.5).

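### Section 7.2.4 derives Youden cut-points and multi-marker logistic models for 1-year survival in the same 24 (at most 40) patients with no optimism correction, so any apparent J or AUC will be inflated; minor, because the analyses are exploratory.

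*Combined protocol and SAP*

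**What the plan says.** Section 7.2.4 (Biomarker Analyses) treats survival at one year as a binary outcome. It regresses that outcome by logistic regression on baseline levels of, and changes in, circulating Treg and MDSC. For the changes, "Optimal cutpoints for changes from baseline will be estimated for the separation of those patients who are alive at 1 year", using the Youden index from the ROC curve. After the tumour PD-L1 and TIL assays it adds: "Additional analyses will combine all of these key biomarkers in logistic models", with the aim of finding candidate combinations. The number of model terms is not given.

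The section opens by calling the correlative work exploratory and too small for a formal test of any marker's prognostic value. Neither it nor Appendix 7 (Research Biomarker/Correlative Studies) mentions cross-validation, bootstrap correction, penalised fitting, a permutation test, a separate validation set or a limit on terms.

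On numbers, the synopsis says of the main cohort: "We will use a single-stage design and enroll 24 patients". Section 3.1.2 says of the surgical cohort: "We will enroll 16 subjects in this cohort". Section 2.2, under the heading covering both cohorts, says: "We will explore the association of 1-yr OS with tumor tissue and circulating biomarkers as described in the exploratory study endpoints". Section 7.2.4 does not say whether the cohorts are pooled for these models.

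**The concern.** A cut-point chosen to maximise separation, and a model fitted by maximum likelihood, both adapt to chance patterns in the data that produced them. Sensitivity, specificity, J or AUC read from those same data are therefore too favourable, and the excess grows as terms are added or patients are fewer. Here the smaller outcome group would hold roughly 8 to 12 patients, so even a six-term model has at most two per term.

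What is at stake is the ranking of markers to carry forward. If noise and signal produce similar apparent performance, the output cannot serve the purpose that Section 2.2 gives it, which is to single out candidate markers of response or resistance.

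**Working it through.** **Inputs from the documents.** Main cohort n = 24, surgical cohort n = 16, so at most 24 + 16 = 40. The synopsis gives the design rates: "a 12 month (1yr-OS) of 35% will be considered non-promising" and "an increase in the 1yr-OS to 60% will be considered promising". Expected numbers alive at one year are:
- n = 24: 24 × 0.35 = 8.4 and 24 × 0.60 = 14.4, so about 8 to 14.
- n = 40: 40 × 0.35 = 14 and 40 × 0.60 = 24.

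**The plan's own figure.** Section 7.2.4 states no figure for the biomarker analyses. The only related one is the design size, n = 24 with 80% power. It reproduces closely with a one-sided 0.05 test: declaring success at 13 or more of 24 alive has exact alpha 0.0423 and power 78.7%, and the arcsine approximation gives 79.8%. Section 7.2.2 says "this design has a two-sided Type I error of 0.05 and a power of 80" per cent. Read as two-sided, n = 24 does not give that power (14 or more of 24: power 65.0%). That is a separate matter and does not affect this point.

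**Assumptions.** Markers are independent, normally distributed and unrelated to survival. The number of terms k is not in the plan. Six is one reading of Section 7.2.4: Treg baseline and change, MDSC baseline and change, PD-L1, TIL. Four and eight are shown on either side.

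**Single cut-point.** J = sensitivity + specificity − 1, maximised over all cut-points with direction free.
- n = 24: mean maximum J is 0.32-0.34, and J reaches 0.5 in 8-13% of simulated trials. Taking the better of two noise markers raises mean J to 0.39-0.40.
- A Fisher test at the selected cut-point, ignoring the selection, gives p < 0.05 in 13-17% of trials against a nominal 5%. That is 13/5 = 2.6 to 17/5 = 3.4 times too often.
- n = 40: mean maximum J is 0.25-0.27.

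**Combined model.** Maximum-likelihood logistic fit with k noise markers; the AUC is computed in the fitting data.

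| k | Apparent AUC, n = 24 | AUC ≥ 0.80, n = 24 | Apparent AUC, n = 40 | AUC ≥ 0.80, n = 40 | AUC in new data |
|---|---|---|---|---|---|
| 4 | about 0.73 | 16-23% | 0.67-0.68 | 3-4% | 0.50 |
| 6 | 0.79-0.80 | 45-49% | 0.71-0.72 | 11-13% | 0.50 |
| 8 | about 0.85 | 72-75% | 0.76 | 26-28% | 0.50 |

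At n = 24 with eight terms, 7-13% of fits separate completely, and maximum-likelihood odds ratios then do not exist.

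**Which correction works.** The true value is 0.50 throughout. The cross-validated figure averages the AUC within held-out folds, using repeated stratified 4-fold splits.

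| n, alive, k | Apparent | Bootstrap-corrected | Cross-validated |
|---|---|---|---|
| 24, 14, 4 | 0.73 | 0.57 | 0.50 |
| 24, 14, 6 | 0.80 | 0.61 | 0.52 |
| 24, 14, 8 | 0.85 | 0.63 | 0.50 |
| 24, 8, 6 | 0.80 | 0.60 | 0.50 |
| 40, 24, 6 | 0.72 | 0.56 | 0.49 |

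Plain bootstrap correction leaves residual optimism at these sizes. Pooled leave-one-out errs the other way: with one or two noise markers at n = 24 it gives about 0.26-0.36. These checks cover AUC from unpenalised fits. Cross-validated J was not simulated separately and is recommended on the same principle.

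**The case against.** The strongest reply is that Section 7.2.4 already limits what may be claimed. It calls the work exploratory, disclaims any formal test, and speaks of potential combinations. No primary or secondary endpoint, go/no-go rule or patient-management step uses these models. That stands, and it sets the severity. It does not remove the bias: the label limits the claim, but the J or AUC remains too high.

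The plan also does not expressly commit to publishing J or AUC. That is true, but a Youden cut-point comes with its J, and a predictive model is hard to present without some measure of performance.

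A reader might infer several stronger things that the documents do not support:
- **That exactly 24 patients are used.** Sections 2.2 and 3.4 assign the biomarker aims to both cohorts, so up to 40 could contribute, with less inflation. Pooling is not specified, and Section 6.11.2 places the follow-up blood sample at C2D1 in the main cohort but at C1D15, after re-resection, in the surgical cohort.
- **That noise markers are bound to look strongly predictive.** With four terms the apparent AUC is only about 0.73, and a J of 0.32 (for example 0.66 + 0.66 − 1) is weak discrimination. An AUC near 0.80 needs about six or more terms in 24 patients, a count the plan neither states nor rules out.
- **That the cut-point itself is biased upward.** Its location is unstable; it is the apparent J and AUC that are biased upward.
- **That the trial would declare predictors where none exist.** The plan sets no rule for declaring one.

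**Conclusion.** The concern holds as a minor point. Cut-points and multi-marker models for one-year survival are to be derived in 24 patients, or at most 40, with no planned means of judging them other than the fitting data. For noise markers at n = 24, the expected apparent AUC exceeds the true 0.50 by about 0.23 with four terms (0.73 − 0.50), 0.29 with six (0.79 − 0.50) and 0.35 with eight (0.85 − 0.50). At n = 40 the excess is about 0.17, 0.21 and 0.26. The naive false-positive rate at a Youden cut-point is roughly tripled at n = 24.

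These sizes rest on independent normal markers, on assumed term counts, and on 8 to 14 patients alive of 24 (14 to 24 of 40). The direction of the bias does not depend on the exact counts. The main result of the trial is unaffected. What is weakened is the use of these analyses to choose markers for later study.

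**What to change.** Amend Section 7.2.4 to:
1. State the analysis set: main cohort alone, each cohort separately, or pooled, and if pooled how the different sampling visits are handled.
2. Fit the combined model with Firth or ridge penalisation.
3. Take any reported AUC and Youden J from repeated stratified k-fold cross-validation, with cut-point selection repeated inside each fold, and add a permutation p-value. Do not rely on plain bootstrap correction or pooled leave-one-out, for the reasons shown in the check.
4. Label every cut-point as needing external validation.

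Naming the intended terms in advance would also help. Restricting the model to one or two markers is not required, since it would give up much of the stated search for combinations.

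The cost is some extra programming and lower reported performance. No additional patients, samples or visits are needed.
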